6.5 Baseline visit

The baseline study visit includes the following items:

(1) Explain study contents and procedures to participant and sign the informed consent form.

(2) Urine pregnancy test (for women of childbearing potential).

(3) Check inclusion/exclusion criteria.

(4) Blood, urine and saliva samples collection (biomarkers).

(5) Genetic testing to examine risk gene *APOE* and known pathogenic genes *PSEN1*, *PSEN2*, and *APP* for all participants.

(6) Collecting participant and informant demographics.

(7) Collecting family history and draw family tree.

(8) Previous medical, medication history and life style.

(9) Physical exam and vital signs.

(10) Neurological Exam.

(11) Neuropsychological test: Mini-Mental State Examination (MMSE), Montreal Cognitive Assessment (MoCA), Neuropsychiatric Inventory Questionnaire (NPI-Q), Hamilton Anxiety Scale (HAMA), Hamilton Depression Scale (HAMD), Modified Hachinski Ischemic Scale (m-HIS), the world health organization university of California-Los Angeles auditory verbal learning Test (WHO-UCLA AVLT), Rey-Osterrieth Complex Figure Test (ROCFT), Digit Span Forward (DSF), Digit Span Backward (DSB), Verbal Fluency Test (VFT), Trail Making Test (TMT) A/B, Boston Naming Test (BNT), Clinical Dementia Rating (CDR), Activities of Daily Living (ADL).

(12) MRI includes the following: conventional scan T1 weighted image (T1WI), T2 weighted image (T2WI), T2 FLAIR and hippocampal scan coronary T1-FLAIR sequence.

(13) ¹⁸F-FDG PET.

(14) ¹¹C-PIB PET.

(15) Carotid ultrasound.

(16) Lumbar puncture to examine cerebrospinal fluid (after MRI exams) and follow-up phone call (if participate in LP)

(17) After informed consent, non-pharmaceutical interventions are carried out on non-onset gene mutation carriers in the family, including lifestyle changes, increased physical exercise and cognitive training, and nootropic drugs.

6.6 Follow-up in-person visits

The follow-up interval will be determined by the age of the individual in relation to the parent's Average Age of Onset (AAO) or pedigree mean AAO. The affected parent's AAO or pedigree mean AAO is used as the index for the frequency of assessments as follows in **Table 1**. In the years between in-person visits, telephone follow-up will be carried out every six months to inquire about cognitive change. If cognitive changes are reported by the participant and/or the informant during the telephone follow-up, the follow-up plan will be advanced and the participant will have a in-person clinical assessment.

Follow-up study visit includes the following items:

- (1) Urine pregnancy test (for women of childbearing potential)
- (2) Blood, urine and saliva samples collection (biomarkers)
- (3) Family history update
- (4) Participant and informant demographics
- (5) Medical and concurrent medications history
- (6) Physical exam and vital signs
- (7) Neurological exam

(8) Neuropsychological test: Mini-Mental State Examination (MMSE), Montreal Cognitive Assessment (MoCA), Neuropsychiatric Inventory Questionnaire (NPI-Q), Hamilton Anxiety Scale (HAMA), Hamilton Depression Scale (HAMD), Modified Hachinski Ischemic Scale (m-HIS), the world health organization university of California-Los Angeles auditory verbal learning Test (WHO-UCLA AVLT), Rey-Osterrieth Complex Figure Test (ROCFT), Digit Span Forward (DSF), Digit Span Backward (DSB), Verbal Fluency Test (VFT), Trail Making Test (TMT) A/B, Boston Naming Test (BNT), Clinical Dementia Rating (CDR), Activities of Daily Living (ADL).

(9) MRI includes the following: conventional scan T1 weighted image (T1WI), T2 weighted image (T2WI), T2 FLAIR and hippocampal scan coronary T1-FLAIR sequence.

(10) ¹⁸F-FDG PET.

(11) ¹¹C-PIB PET.

(12) Carotid ultrasound.

(13) Lumbar puncture to examine cerebrospinal fluid.

Table 1 Follow-up visit plan and frequency

Index: Individual compared with parent's AAO or pedigree mean AAO	In-person assessment interval
> 10y younger	every 5 years
10y – >3y younger	every 3 years
3y – 0y younger	annual
0y – <3y older	annual
≥ 3y older	once, at 5 years older than parent's AAO
*Documented cognitive decline on telephone follow-up, confirmed by an in-person clinical assessment	every six months

Telephone follow-up will occur as indicated in the schedule of events in order to maintain contact with the family, inquire about cognitive change, and update information about adverse effect.

7. Assessments

7.1 Clinical evaluation

7.1.1 Demographic data (Appendix 1)

The demographic data should be filled in as completely as possible, including date of birth, age, family address, contact information, education level.

7.1.2 Current medical history

The detailed and objective current medical history must be filled out by the physicians. If case report form (CRF) cannot describe the symptoms and characteristics of the subject in detail, fill in the blanks.

Describe the specific manifestations of cognitive impairment, such as the specific manifestations of memory impairment (nearly/distant/ semantic forgetting); the specific manifestations of language barriers (difficulty in finding words, understanding, expressing, naming, writing, etc.); specific manifestations of disorientation (time, place, people, etc.); specific manifestations of personality and mental behavior (apathy, withdrawal, depression, agitation, wandering, abnormal sleep, antisocial behavior such as theft, etc.); the specific forms of hallucinations such as visual hallucinations, auditory hallucinations, etc.); manifestations of dyskinesia (such as ataxia, Parkinson-like dyskinesia, involuntary movements, etc.); implementation of dysfunction; spatial skills decline and other specific performance.

Physicians should describe the extent of decline in each cognitive domain, whether cognitive impairment affects the patient's daily ability and social function, and how it behaves.

7.1.3 Past history

According to the current internationally recognized diagnostic criteria, the previous illness of the subject is diagnosed or confirmed, and the presence or absence of the relevant disease, the time of diagnosis and the course of the disease are recorded in detail. Diseases with significant neurological sequelae, history of general anesthesia, and history of radiotherapy as well as chemotherapy need to be documented in detail. Try to let the subject or family provide the hospital's medical record/diagnostic certificate, etc., or the investigator will retrieve the patient's past medical records for inspection and confirmation.

7.1.4 Medication situation

The subject's medication needs to be documented in detail, including the name of the medication for the treatment of cognitive impairment and other diseases, the frequency of administration, and the adherence of the medication. Try to have the subject present a medical record, drug package or prescription.

7.1.5 Family history and family diagram drawing

For subjects with a family history, the investigator should investigate in detail the incidence of each member of the family, and generally investigate the three generations of relatives of the patient. For cognitive impairment and suspected cognitive impairment in the family, the disease should be recorded in detail (e.g. age of onset, first symptom, progression of disease, involvement of each cognitive domain, age of dementia, diagnosis and treatment, clinical consistency with the proband, etc.). Refer to operation manual for the rules of family diagram drawing.

7.1.6 Physical examination

Physical examinations include general medical examinations and neurological examinations performed by senior neurologists.

7.2 Psychometrics

7.2.1 Mini Mental State Examination (MMSE) [39] (Appendix 2)

MMSE is simple and easy to use, widely used at home and abroad, and is the preferred scale for dementia screening. The scale includes the following seven aspects: time orientation, location orientation, immediate memory, attention and calculations, delayed memory, language, and visual space. There are 30 items. The total scores range from 0 to 30. Test scores are closely related to cultural level.

7.2.2 The Montreal Cognitive Assessment (MoCA) [40] (Appendix 3)

MoCA is designed as a rapid screening instrument for mild cognitive dysfunction. It was created in 1996 by Ziad Nasreddine in Montreal, Quebec. It assesses different cognitive domains: attention and concentration, executive functions, memory, language, visual constructional skills, conceptual thinking, calculations, and orientation. Time to complete the MoCA is approximately 10 minutes. The total score is 30; a score of 26 or above is considered normal.

7.2.3 Neuropsychiatric Inventory (NPI-Q) [41] (Appendix 4)

The NPI-Q is a well-validated, reliable, multi-item instrument to assess neuropsychiatric symptoms in AD based on an interview with an informant (caregiver). The interview is relatively brief (<15 minutes). It evaluates both the presence and severity of 12 neuropsychiatric features, including delusions, hallucinations, agitation, dysphoria, anxiety, apathy, irritability, euphoria, disinhibition, aberrant motor behavior, night-time behavior disturbances, and appetite and eating abnormalities. The questionnaire separately evaluates the frequency and severity of each abnormal psychiatric symptom and the degree of distress of the caregiver. The caregiver is asked to rate the frequency of the symptoms of that domain on a scale of 1 to 4 (1 = occasionally, less than once per week; 4 = very frequently, once or more per day or continuously) as well as their severity (1 = mild, 2 = moderate, 3 = severe). The total score for each domain is calculated by multiplying the frequency by the severity. A total score is calculated by adding all the domain scores together. Caregiver distress is rated by the caregiver on a six-point scale from 0 (no distress) to 5 (very severe or extreme distress). Finally, the total score of all the symptoms of the caregiver's distress is obtained separately.

7.2.4 Hamilton Anxiety Rating Scale (HAMA) [42] (Appendix 5)

The HAMA is a psychological questionnaire used by clinicians to rate the severity of a patient's anxiety. The scale [43] consists of 14 items designed to assess the severity of a patient's anxiety. Each of the 14 items contains a number of symptoms, and each group of symptoms is rated on a scale of 0

to 4, with 4 being the most severe. All of these scores are used to compute an overarching score that indicates a person's anxiety severity [44]. Upon the completion of the evaluation, the clinician compiles a total, composite score based upon the summation of each of the 14 individually rated items. This calculation will yield a comprehensive score in the range of 0 to 56. It has been predetermined that the results of the evaluation can be interpreted as follows: A score of 17 or less indicates mild anxiety severity. A score from 18 to 24 indicates mild to moderate anxiety severity. Lastly, a score of 25 to 30 indicates a moderate to severe anxiety severity.

7.2.5 Hamilton depression scale (HAMD) [45] (Appendix 6)

The HAMD is a multiple item questionnaire used to provide an indication of depression. Max Hamilton originally published the scale in 1960 [45] and revised it in 1966 [46], 1967 [47], 1969[48], and 1980 [49]. The questionnaire is designed for adults and is used to rate the severity of their depression by probing mood, feelings of guilt, suicide ideation, insomnia, agitation or retardation, anxiety, weight loss, and somatic symptoms. The original 1960 version contained 17 items (HDRS-17). Each item on the questionnaire is scored on a 3 or 5 points scale. The total score can be used to evaluate the severity of depression and treatment effect. The milder the symptoms, the lower the total score, and the severer the symptoms, the higher the total score. Assessment time is about 20 minutes.

7.2.6 Modified Hachinski ischemic scale (m-HIS) [50] (Appendix 7)

The m-HIS can be used to identify vascular dementia through clinical findings. The scale has 8 items with a total score of 12 points. If there are step worse, telling physical symptoms, emotional loss, and history of hypertension, score 1 point each; if there are acute onset, history of stroke, focal symptoms of the nervous system, focal signs of the nervous system, score 2 points each. The total score ranges from 0 to 12. The higher the score, the greater the likelihood of vascular dementia; those with a score of 4 or less are AD; those with a score of 7 or more are vascular dementia.

7.2.7 The world health organization university of California-Los Angeles auditory verbal learning Test (WHO-UCLA AVLT) [51] (Appendix 8)

This test was originally developed by the World Health Organization to be used in international research. The WHO-UCLA AVLT includes immediate recall, delayed recall, and delayed recognition. The process is as follows: The tester reads 15 words while informing the subject that they need to immediately recall after listening. Learning and recalling 3 times, after about 30 minutes interval, delayed recall test of 15 words without prompting. Then the tester reads 30 words (including 15 learned words and 15 interference options). The subject is asked to judge whether it is a learned word, and the number of correct words is recorded. This is a recognition test. The scale examines the ability to enter, store, extract, pay attention, and vocabulary of memory, and the score increases with increasing educational level.

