4.5 Biomarkers of FAD in China

We will conduct neuropsychological tests, clinical examinations, and imaging examinations on members of the FAD family, and conduct regular cerebrospinal fluid and blood sample collections. Use the international standardized electronic patient registration system to establish a large-scale and high-quality clinical information database and biological sample database to provide a foundation and platform for the establishment of the AD diagnosis system and risk prediction model. We will also focus on the asymptomatic mutant gene carriers in FAD families and analyze the changes of various imaging and body fluid markers in normal cognitive, Pre-MCI, MCI, AD and other stages.

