4.5.1 Body fluid markers

Firstly, by collecting biological specimens of FAD family members, including blood, cerebrospinal fluid, urine and saliva etc., and referring biological sample banks of people in different clinical stages, the study can effectively identify highly sensitive and highly specific body fluid markers in different clinical stages of AD. Furthermore, longitudinal follow-up of people in different clinical stages of the family, detect AD potential and newly developed biomarkers in body fluids at baseline, and then combined with clinical neuropsychological evaluation, to establish a diagnosis system for AD clinical stages. Moreover, conduct regular follow-up and collection of body fluid samples in the included research cohort to monitor the dynamic changes of body fluid markers of patients as the disease progresses. Finally, combined with individual factors, clinical characteristics, neuropsychological assessment and body fluid markers, a comprehensive risk analysis of the entire disease process of AD occurrence and development was carried out, and body fluid marker prediction models in different stages of AD pathogenesis were established.

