7.4 Imaging

A model of how different AD biomarkers change during the development of the AD proposed that biomarkers became abnormal in the following order:

- (1) β -amyloid (indicating deposition of amyloid in plaques outside the cell, measured in CSF and by amyloid PET)
- (2) Tau (indicating the formation of tau fibrils with the neurons)
- (3) Glucose metabolism (measured on PET, indicating damage to neurons)
- (4) Structural MRI (indicating damage to brain structure)
- (5) Cognitive impairment

At the time of each assessment, participants will undergo scanning with MRI and PET. The PET imaging will include both FDG and PIB scans to measure metabolism and $A\beta$ deposition, respectively.

Xuanwu Hospital and each sub-center have advanced imaging equipment, including cyclotron RDS111 (Siemens) and GE's PET/MR full body scanner. It has the license for the use of radioactive drugs by the National Food and Drug Administration (the fourth category) and has the qualification to prepare new drugs (tracer) for research and development.

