7.4.3 Carotid ultrasound

Carotid ultrasound can clearly demonstrate the vascular intima-media thickness, the location and size of plaque, the degree of vascular stenosis, and analyze hemodynamics. It plays a key role in the assessment and diagnosis of vascular-related diseases caused by atherosclerosis. Carotid ultrasound examination should be performed within 1 month before or after neuropsychological examination (with no new vascular disease event). An experienced ultrasound physician is required to perform the operation according to "Guidelines for Carotid Ultrasound Examination". Longitudinal and transverse

section scanning are performed from frontal and lateral directions. Observe and record the peak systolic velocity (PSV), end diastolic velocity (EDV), intima-media thickness (IMT) and plaque (diameter, number, acoustic properties) of internal carotid artery, common carotid artery and carotid bifurcation.

8. Statistical analysis

Periodic review of the accumulating data will be made to safeguard the statistical quality of the data and to ascertain whether they conform to the expectations of the original statistical design. At the same time, the statistician will perform statistical quality control of FAD data, focusing on outlier and missing data detection and comparison among sites. Then, the statistician will participate in statistical data analyses, consultations and reporting using R software and other statistical software, such as SAS and SPSS for specialized statistical analyses. The sample size is calculated using the paired sample t test, and the statistical test level is set to 0.05.

The normality and homogeneity of variance tests were performed on continuous variables. Data that passed these two tests were presented as mean \pm standard deviation, then underwent t-testing for comparisons between two groups and one-way analysis of variance (ANOVA) testing for comparisons among three or more groups. After ANOVA analysis, a Dunnett's multiple comparison test was used for post hoc testing. Data that did not pass the normality test were presented as quartiles, and underwent nonparametric testing, using the Kruskal-Wallis test and Dunn's multiple comparison test for comparisons among three or more groups. The significance of differences was assessed by the χ^2 test for categorical variables. The correlation between variables were calculated using Pearson or Spearman method.

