For the longitudinal repeated data, to explore the correlation between different markers and AD, a Bayesian linear mixed model was used to model each marker as a function of estimated years from expected symptom onset (EYO) and mutation status (carrier or noncarrier). The fixed effects included sex, age, follow-up time, mutation status, EYO, and their two-way interaction.

9. Data management

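### CRF item A6 pools all schooling above 6 years, although the protocol ties cognitive scores to education and makes education a study aim, and the group tests named in Section 8 do not adjust for it

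*Protocol*

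**What the plan says.** Two of the cognitive tests are described as depending on schooling or background. Section 7.2.7 states of the WHO-UCLA AVLT that "the score increases with increasing educational level". Section 7.2.1 states of the MMSE: "Test scores are closely related to cultural level".

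Sections 3.2 and 4.2 list education level among the factors whose effect on the occurrence and development of the disease is to be clarified, alongside region, age and rural or urban living. Section 7.1.1 names education level as a demographic item but gives no unit. The form behind it, Appendix 1 item A6, has three tick boxes: less than 1 year, 1 to 6 years, and more than 6 years.

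For comparisons of continuous variables, Section 8 names t-tests for two groups, "one-way analysis of variance (ANOVA) testing for comparisons among three or more groups" with Dunnett's test, and Kruskal-Wallis with Dunn's test where normality fails. None of these is given a covariate. For repeated measurements it names one Bayesian linear mixed model, fitted to each marker: "The fixed effects included sex, age, follow-up time, mutation status, EYO, and their two-way interaction". Education is not in that list.

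**The concern.** The protocol identifies schooling as a determinant of its own outcome measures and also makes it an exposure of interest, but records it on a scale whose top category has no upper end. Someone who left school soon after the sixth year and someone with a university degree receive the same code.

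Two things are at stake. First, the education aim can distinguish only none, primary-length and everything longer. Second, where groups differ in schooling, part of an observed difference in test scores reflects schooling rather than disease, region or residence. The tests named in Section 8 do nothing to separate the two, and a larger sample does not remove a bias. The coding matters more than the choice of test, because a test can be changed at analysis while unrecorded years cannot be restored.

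**Working it through.** The protocol gives no figure that depends on education, so there is none to reproduce. The check is a reading of the passages against each other, with the bias written in symbols.

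**1. Does score depend on schooling?** Yes for the AVLT, in so many words (7.2.7). For the MMSE the protocol says cultural level (7.2.1), which points the same way.

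**2. What is recorded?** A6 is the only education item on the Appendix 1 form. The CDR interview in Appendix 15 also asks for the last school attended and the grade, once of the informant and once of the participant. Both questions stand among the memory questions and serve to test recall; they do not record completed years.

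**3. What does an unadjusted test estimate?** Suppose score rises by *b* per year of schooling, and groups 1 and 2 do not otherwise differ. With mean years E1 and E2, the expected difference in mean score is

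bias (unadjusted) = *b* × (E1 − E2).

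This is nil if schooling is balanced, and it does not shrink with sample size.

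**4. What does adjustment for the A6 bands leave?** With E1k and E2k the mean years inside band k, and weights w_k that sum to 1,

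bias (after A6) = *b* × Σ w_k × (E1k − E2k).

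Only differences inside a band remain. In the lowest band they are under 1 year. In the middle band they are at most 6 − 1 = 5 years. In the top band the form sets no limit. The more participants fall in the top band, the less the item can adjust for; if all did, it would be a constant and adjust for nothing. Completed years, entered as a number, would remove the bias to the extent that the relation is linear.

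**5. Which inputs do the documents supply?** Neither *b* nor the distribution of schooling in any group. The size of the bias therefore cannot be calculated from the protocol.

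**6. Which contrasts are exposed?**
- Carriers against noncarriers in the same pedigree: little exposed, since inheritance of the mutation does not depend on schooling and relatives share background.
- Change within a person: little exposed, since a constant shift from schooling cancels in the difference.
- Clinical stages, generations, regions, rural against urban residents: exposed wherever schooling differs between the groups.

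**7. Does the longitudinal model cover cognitive scores?** The text leaves this open. Section 4.5 uses the word for fluid and imaging measures: the plan there is to "analyze the changes of various imaging and body fluid markers in normal cognitive, Pre-MCI, MCI, AD and other stages". Section 7.4 describes a model in which "biomarkers became abnormal in the following order", with "5) Cognitive impairment" as its last entry, but that is background to the imaging section and not a list of analysis variables. Section 4.4 plans baseline and follow-up analysis of cognitive function without naming a model.

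**The case against.** The strongest reply is that covariates are a matter for the statistical analysis plan, which is not shown. Section 8 is a generic list; it assigns no test to the AVLT or the MMSE and does not say that scores will be compared only without adjustment. That stands in part. It is why the second half of the point is conditional: the comparisons would be confounded if run as written. It does not answer the first half, because an analysis plan can add a covariate but cannot recover years from a tick box.

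A second reply is that section 4.5.1 plans to use "combined with individual factors, clinical characteristics, neuropsychological assessment and body fluid markers, a comprehensive risk analysis", and section 4.2 counts sociodemography among individual factors, so education may enter there. It may, but the input would still be A6.

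A third is that sections 3.2 and 4.2 ask about occurrence and development of disease, not about test scores compared across regions. This is fair. Such comparisons are plausible uses of the data; they are not specified contrasts. The coarse item still limits the education aim itself.

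A reader might go further and infer that the mixed model is misspecified because education is absent. The documents do not support that. If the model is for fluid and imaging markers, the statements about the AVLT and MMSE give no reason to add education to it. A reader might also infer that the carrier/noncarrier results or the emphasis on conversion from the asymptomatic stage are compromised. Those are the contrasts least exposed.

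**Conclusion.** The point holds in a limited form. A6 is too coarse for an aim the protocol states and for adjusting scores that the protocol itself links to education or cultural level, and the loss cannot be repaired at analysis. The unadjusted group tests would confound cognitive-score comparisons between groups that differ in schooling. This rests on the protocol's own statement that score rises with education and on the assumption that such groups will be compared on cognitive scores.

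A reader might infer that the bias is large. Nothing in the documents shows this: its size depends on a slope and on schooling distributions that are not given, and it is nil under balance. No stated sample size, eligibility rule or carrier/noncarrier conclusion is shown to be wrong. It is a cheap improvement to data capture and analysis, worth making because section 2.3 has the study running to January 2038 or longer.

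**What to change.** 1. Change A6 to completed years of education, entered as a number, from now on. Keep the existing band for older records unless an informant or a document supplies the years. Do not fill them from the participant's own answers to the CDR memory questions: these may be wrong because of impairment, which would add error related to cognition.
2. In Section 8, compare cognitive scores between groups with a linear model including age, sex and education, in place of the unadjusted tests.
3. State whether the mixed model is applied to cognitive scores, and add education to its fixed effects only if it is.

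The cost is one CRF field change across the 68 centres, a few lines in Section 8, and no extra visits. The downside is mixed resolution: older records hold a band and newer ones a number, so analyses across both will need a rule for combining them, and residual confounding will remain in the records that hold only a band.
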